-Risk of the blinding: blinding is one of the major challenges of the trial. It will be performed in each site using a secured research picture archiving and communication system (PACS) thanks to radiologist engineering. To allow for compliance and smooth running of the study, all ED and radiology staff will be regularly informed regarding methods and stakes. As soon as the patient is included, the research staff will anticipate and inform the radiology staff who will take care of the patient, and the clinician to perform LUS about the necessity of blinding and the CRF to fill in. The research staff will be the only one able to provide the attending clinician with the result of the allocated imaging modality, and ensure that it is accessible in the patient's medical record. The two other imaging modalities will be concealed until day 5, and will only be accessible on the PACS.

According to a predefined list of emergency findings, the radiologist interpreting CXR or LDCT or the clinician performing LUS will be able to immediately ask the investigator for unblinding.

At day 5, the research staff will ensure that the two blinded imaging modalities are made accessible again to the treating clinician.

-The risk of a false negative (meaning a missed diagnosis of pneumonia) will be counterbalanced by the fact that the clinician will be allowed to prescribe antimicrobial therapy for another diagnosis than pneumonia. As patients with severe pneumonia will not be included, a delay of a few hours in the diagnosis of pneumonia is unlikely to lead to an unfavourable outcome. Indeed, a longer time to antibiotic administration was not associated with an unfavourable outcome in moderately severe CAP (53).

-The panel of experts: we already used the Delphi method with a panel of experts for the reference diagnostic in our previous study. The panel of experts will be composed by board-certified specialists in infectious diseases, respiratory diseases, internal medicine and radiology. All will be senior attending physicians with expertise in caring for patients with pneumonia. They will be previously trained for the diagnosis of pneumonia using international and Swiss guidelines. They will have access to all imaging studies, to avoid any potential incorporation bias.

-Coordination: as this is a multicentre and multidisciplinary trial, particular emphasis will be put on coordination.

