Finally, we estimated that risks inherent to the trial are minimal and inferior to the benefits of the study which could deliver key results which would provide long-term benefit to all patients with pneumonia.

Sequential realization of the 3 imaging modalities may delay the final working diagnosis of the physician in charge. However, this delay will be minimized by the research staff, who will make any effort to guarantee quick delivery of all diagnostic procedures. As severe pneumonia will not be included, a delay of at most a few hours before adequate treatment is not expected to have a negative impact on patients' evolution (54). All imaging must be done before leaving the ED. A transfer from one ED to another is not considered as an exit from the ED (e.g. a transfer of the 3-Chêne to Cluse-Roseraie for Geneva)

Methods of minimising bias:

-Stratified randomization will be used in this study.

-Allocation sequence

Participants will be randomized 1:1:1 to either the CXR, the LDCT, or the LUS arm as per a computer-generated randomization schedule stratified by study centre using investigator blinded randomly permuted blocks of varying size.

-Concealment mechanism

Patients will be randomized via eCRF directly.

-Implementation

An independent statistician will create confidential randomization lists for each site. The lists will be given to the data-manager to implement the randomization list in the eCRF. Each site will have a dedicated research staff responsible for approaching patients attending the ED regarding inclusion in the study. The triage nurses and the physician working at the ED will also be asked to help the study team by alerting the research staff to the presence of any potential participant. The site's coinvestigator(s) will also be on hand to answer any additional questions the patient might have. If the patient agrees to participate in the study, the patient's written informed consent will be obtained and the study coordinator randomized the patient directly through the eCRF. The research staff will keep the "crosswalk", a table linking the participant's randomization number with his/her identifying data, in a locked document.

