A panel of experts will adjudicate the final diagnosis in all patients, having access to all data (clinical, CXR, LDCT and LUS and outcome data at day 28), while blinded to the allocation arm. Their diagnosis will be considered as the reference diagnosis.

Safety: Number of death and admissions to the ICU in each arm will be communicated to a dedicated data safety monitoring board after 200 inclusions for a safety interim analysis.

Blinding of the imaging modalities: For each patient, the two blinded imaging modalities will be registered on a secured PACS. The CRFs filled for these imaging modalities will be kept unavailable as well as images until day 5.

Unblinding: The research staff will ensure that unblinding of imaging and CRFs is done at day 5 and that all results are available in the electronic health record.

Unblinding will be performed **in emergency** at the ED if the radiologist/clinician performing LUS diagnoses immediately life-threatening findings: pneumothorax, pleural effusion in large quantities (white lung) with mediastinal shift, complete atelectasis of one lung, indirect sign of aneurysmal rupture (haemomediastinum), massive pericardial effusion, tracheal foreign body, pneumoperitoneum, haemothorax, pneumomediastinum, suspicion of acute tuberculosis (NB: pulmonary embolism won't be excluded as LDCT will be performed without intravenous contrast).

In case of such finding, the radiologist interpreting CXR or LDCT and the clinician performing LUS will call in emergency the investigator to be allowed to communicate the results to the clinician.

In case of subsequent clinical deterioration, the clinician in charge of the patient may prescribe any new imaging deemed necessary: a new CXR for the diagnosis of heart failure; injected chest CT scan to eliminate a pulmonary embolism or a suppurative complication.

Nevertheless, the local investigator will be accessible and able to proceed to a deblinding in justified cases.

GEROBIOTA

At admission:

-Microbiota samples (saliva and respiratory samples) before antibiotic administration at the ED if possible. They will be stored at -80.

NB: respiratory samples will be those taken for routine methods including sputum, induced sputum, tracheal aspirate or broncho-alveolar lavage if done and still available

-Blood: Serum (2 tubes), plasma EDTA (2 tubes), plasma citrate (2 tubes), PAX gene DNA (1 tube), PAX gene RNA (1 tube).

During hospitalization:

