#### **Physician in charge**

The treating physician was aware of the allocation group. However, he was blinded to the results of the two non-assigned radiological examinations, which were concealed for 5 days. The examinations to be masked were known to the research staff immediately after randomisation. Emergency unblinding was permitted in the occurrence of an immediately life-threatening finding (see Box 2).

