#### **Panel of experts**

The panel of experts was consulted only after the completion of patient recruitment and had access to all data (clinical information and outcome data), including the results of all radiological examinations (CXR, LDCT, and LUS). However, each expert was blinded to the allocation group and to the final evaluation made by the physician in charge (published in ClinicalTrials.gov).

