## Methods

### 1/ Panel constitution

The experts will be randomly assigned to a pair. Each pair will include one expert from the study staff and a second expert not involved in the study.; The pair same pair will assess the patients on round one and two.

Both experts must be physicians in current clinical practice (at least part-time); they must be regularly confronted with patients with a suspicion of pneumonia; they must be board-certified in internal medicine, infectious disease, lung disease, intensive care medicine, or emergency medicine; and they must have at least 5 years of clinical experience.

Radiological experts who will attend the 3rd round of the adjudication will be board-certified in radiology and experienced in thoracic imaging. Ultrasonography experts will also be present, they will be board-certified.

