### 3/ Blinding of any index test

Not feasible in this study, but experts will be blinded to the randomization arm and to the diagnosis of clinician at the emergency room.

If the experts have been involved in routine clinical care, they will only adjudicate cases that they had not previously treated

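### The expert panel's recusal rule covers patients treated in routine care but not patients handled in a trial role, so blinding of the reference diagnosis to arm is stated but not secured

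*SAP*

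**What the plan says.** The panel method appended to the SAP (1/ Panel constitution) says: "Each pair will include one expert from the study staff and a second expert not involved in the study". The same pair rates a patient in rounds 1 and 2. Cases still discordant go to a plenary third round of all experts, whose consensus is the reference diagnosis.

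On prior contact there is one rule (3/ Blinding of any index test): "If the experts have been involved in routine clinical care, they will only adjudicate cases that they had not previously treated".

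SAP 3.8 states the blinding as achieved: "each expert was blinded to the allocation group and to the final evaluation made by the physician in charge". The bias-reduction list in protocol 4.3 says the same of the panel. It adds that the investigators are blinded to arm.

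The roles that touch allocation are described elsewhere:

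- Protocol 3.3: "the study coordinator randomized the patient directly through the eCRF".
- Protocol 3.3: "The research staff will be the only one able to provide the attending clinician with the result of the allocated imaging modality".
- SAP 3.8: "The examinations to be masked were known to the research staff immediately after randomisation".
- Protocol 4.2 and 4.3: the investigator and research staff approach patients, and research staff follow them daily in hospital and release the masked results at day 5.
- Protocol 4.3: the investigator is called to authorise emergency release of a masked finding, and on later deterioration "the local investigator will be accessible and able to proceed to a deblinding in justified cases".

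SAP 8.1.1 makes the panel's dichotomised rating the reference for the primary outcome.

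**The concern.** The recusal rule accepts that earlier contact with a patient can disqualify an adjudicator, but it is limited to routine care. In this trial, knowledge of the arm arises through trial work rather than routine care alone, and half of every pair is drawn from study staff.

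The clinician's rating is fixed before the patient leaves the emergency department. Whatever then moves the reference differently by arm moves the primary contrast. An adjudicator who knows the arm need not know the clinician's rating to do this. It is enough to give more weight, in a borderline case, to the report of the modality the clinician saw. The positive/negative cut lies between *possible* and *unlikely*, where such cases fall.

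**Working it through.** **1. Roles against the recusal rule**

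| Trial role | Held by | What it can reveal | Covered by recusal? |
|---|---|---|---|
| Approach and enrolment | Investigator and research staff | Not the arm itself; the arm if the same person continues into randomisation | No |
| Randomisation in the eCRF | Study coordinator | Arm | No |
| Masking, delivery of the allocated result | Research staff | Arm | No |
| Daily follow-up, day-5 release | Research staff | Arm, from which result is open in the first 5 days | No |
| Authorising release of a masked result | Investigator | At least that this modality was not the allocated one | No |
| Routine clinical care | Treating physician | Arm | Yes |

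Only the last row is covered.

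**2. Whether another measure closes the gap**

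- *Investigators declared blinded (protocol 4.3).* The same section has the investigator authorise release of masked results, so the general statement cannot hold for those patients.
- *Recoded exports without assignment (protocol 4.3).* These go to an outcomes assessor and the analyst. Round 2 of the panel uses raw images, and round 3 uses physician notes and discharge letters. Recoding does not reach these.
- *Adjudication after recruitment ended (SAP 3.8).* This makes recall less likely but does not exclude it.
- *An uninvolved partner in each pair.* This limits one expert's influence. But discordant cases are settled by discussion and then consensus, in which the study-staff expert takes part.
- *SAP 8.2.2.5.* It changes the cut on the rating scale only. No planned analysis of the primary contrast tests dependence on who adjudicated.

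**3. Size, as an illustration only**

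Inputs from SAP 3.5: accuracy 68% (CXR) and 84% (LDCT), two-sided 0.05, power 90%, 150 per arm. The plan's figure reproduces with a pooled-variance formula:

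n = [1.96·√(2·0.76·0.24) + 1.282·√(0.68·0.32 + 0.84·0.16)]² / 0.16² = (1.184 + 0.760)² / 0.0256 ≈ 148, against 150 stated.

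Now assume no true difference and a shift b in apparent accuracy in the LDCT arm alone. With p₂ = p + b and p̄ the mean of p and p₂:

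- SE₀ = √(2p̄(1−p̄)/150)
- SE = √([p(1−p) + p₂(1−p₂)]/150)
- P(p<0.05) = Φ((b − 1.96·SE₀)/SE) + Φ((−b − 1.96·SE₀)/SE)

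For p = 0.68 and b = 0.02, SE₀ and SE are both 0.0534. The result is Φ(−1.586) + Φ(−2.335) = 0.056 + 0.010 = 6.6%.

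| b (points) | Net patients of 150 (150·b) | Base 68% | Base 76% |
|---|---|---|---|
| 0 | 0 | 5.0% | 5.0% |
| 2 | 3 | 6.6% | 7.0% |
| 3 | 4.5 | 8.7% | 9.5% |
| 5 | 7.5 | 15.8% | 18.3% |
| 8 | 12 | 33.8% | 41.0% |

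Every b here is assumed. The table shows how few references would matter, not how many were affected.

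**The case against.** The strongest reply is that the roles are distinct. The documents give randomisation to a coordinator, masking to research staff and unblinding to the investigator. They nowhere say that the panel's study-staff experts are these people. Panel experts must be board-certified physicians in practice with at least five years' experience, so they may well be investigators, whom the protocol calls blinded. This stands as far as it goes: a reader might infer that the staff who randomise and mask also adjudicate, and the documents do not support that. It does not restore the safeguard. SAP 8.1.2.2 describes the adjudicating expert as an investigator too, and investigators help approach patients and authorise unblinding.

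A reader might also infer a size. With three equal centres and study-staff experts spread as the patients are, 495/3 = 165 cases would have a same-centre expert. Only two of three arms enter the primary contrast, so that is 165·2/3 = 110 cases, 55 per arm. Even this is unsupported. Recruitment was competitive, no rule allocating cases to pairs is given, and working at the enrolling centre is not the same as handling that patient. No share of tipped references can be derived either.

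Finally, adjudication came late, an external expert sits in each pair, and experts are separately blinded to the clinician's rating. These reduce the risk, and the claim that the primary contrast is biased would go too far.

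**Conclusion.** The point holds as a gap in the rules. Blinding of the reference to arm is asserted in both documents, but nothing stops a study-staff expert from adjudicating a patient whom he or she handled in a trial role that can reveal the arm. The gap concerns the primary outcome, so it is worth closing before database lock.

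No breach is shown, and neither the size nor the direction of any bias can be stated. The false-positive figures rest on an assumed shift in one arm, 150 patients per arm, no true difference and an unstratified normal approximation. If the study-staff experts had no such role in the cases they judged, a sentence saying so would settle the matter.

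**What to change.** State in the panel method which trial roles the study-staff experts held. Extend the recusal rule to any patient in whose enrolment, randomisation, masking, follow-up or unblinding the expert took part, and apply it in rounds 1 and 2 and in the plenary. One way is to give study-staff experts cases from other centres and have them abstain on their own cases in the plenary. Reassigning pairs alone would leave round 3 open, because all experts vote there on the disputed cases.

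If adjudication is complete, report by arm the number of cases with such an overlap, including in the plenary. Add to SAP 8.2.2.5 a sensitivity analysis of the LDCT-CXR contrast without those cases. An analysis taking the external expert's round 1 rating as reference can be supportive only. Round 1 lacks raw images and notes, so the information changes along with the rater.

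The cost is minor assignment work, or one analysis with somewhat less precision. At the planned accuracies the standard error of the difference is √(0.352/150) = 4.8 points. If 10% of cases were excluded (an assumed share), it would be √(0.352/135) = 5.1 points.

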### 2/ Information available to the panel

1st round: clinical results; biological tests; microbiological tests; imaging interpretation report (level of probability), data on evolution (length of hospitalization, antibiotic treatment, outcome).

2nd round: previous data + access to the raw images of CXR, CT and US.

3rd round: previous data and raw documents (physician notes, discharge letters, etc).

### 3/ Blinding of any index test

Not feasible in this study, but experts will be blinded to the randomization arm and to the diagnosis of clinician at the emergency room.

If the experts have been involved in routine clinical care, they will only adjudicate cases that they had not previously treated

### 4/Decision making process

#### a) *Definition of CAP*

« An acute illness with cough and at least one of new focal chest signs, fever >4 days or dyspnoea/tachypnoea, and without other obvious cause (...) supported by chest radiograph findings of lung shadowing that is likely to be new. In the elderly, the presence of chest radiograph shadowing accompanied by acute clinical illness (unspecified) without other obvious cause. » (Guidelines for the management of adult lower respiratory tract infections, Clin Microbiol Infect 2011 Nov;17 Suppl 6:E1-59. doi: 10.1111/j.1469-0691.2011.03672.x).

*3 mains components:*

-Acute illness (<21 days).

-Respiratory and infectious findings (or geriatric syndrome in the elderly): cough, dyspnoea, expectorations, chest pain, fever/hypothermia, tachypnoea, hypoxemia.

CAVE In elderly patients, delirium, falls (geriatric syndromes) may reveal an infection.  
(DOI:10.1016/j.ejim.2025.02.025)

-Radiologic demonstration of an invasion of lung parenchyma.

Additionally: not explained by another process (caution with acute exacerbation of COPD; acute decompensated heart failure; pulmonary embolism; lung cancer; diffuse lung disease; large pleural effusion with atelectasis), but concomitant diagnoses are possible.

*Supporting information:*

Elevated CRP (> 30 mg/L); elevated procalcitonin not required because we aim to include viral pneumonia; leukocytosis, neutrophilia, leukopenia.

Identification of a bacterial pathogen known to cause pneumonia thanks to blood cultures, respiratory samples, urinary antigens (*Streptococcus pneumoniae*, streptococci other than *S. pneumoniae*, *Mycoplasma pneumoniae*, *Haemophilus influenzae*, *Legionella* spp, *Moraxella catarrhalis*, *Chlamydia psittaci* or *Chlamydia pneumoniae*, *Coxiella burnetii*, *P. jirovecii* in immunocompromised patients.

Caution with *Staphylococcus aureus*, *Pseudomonas aeruginosa*, other as Enterobacteriaceae (can be a contamination, but can be causative agent of CAP in elderly patients)).

Identification of viruses on naso/oropharyngeal swabs.

*b) Format of the result: Likert scale with 5 levels*

**Pneumonia very likely or confirmed** (more than 90% of probability)

Typical clinical and radiological presentation but no pathogen identified or pathogen not specific to pneumonia (e.g. *S. aureus*; streptococci other than *pneumoniae*)

Typical pathogen identified with any acute lung infiltrate.

**Pneumonia probable** 67-90% of probability)

Imaging suggestive of pneumonia, but a chronic lung condition or heart failure is also present; however, pneumonia probably explains most of the clinical findings

**Pneumonia possible** (34-66% of probability)

Imaging compatible with pneumonia, but another disease could as well explain the findings (acute heart failure with moderate inflammatory biomarkers; known diffuse lung disease with acute symptoms and worsening radiology, known lung cancer with acute symptoms and worsening radiology). However, most clinicians would probably choose to treat with antibiotics.

**Pneumonia unlikely** (10-33% probability)

Imaging compatible with pneumonia, but another disease may better explain the image (pulmonary embolism with lung infarction; large atelectasis with few findings of acute infection).

**Pneumonia excluded** (less than 10% of probability):

No infiltrate on all imaging studies

Faint infiltrate or imaging suggestive of an acute lung condition (heart failure, nodules / mass...), AND another disease is evident (abdominal or urinary sepsis; acute heart failure; cancer)

Response to antibiotic treatment should be considered with caution because of frequent concomitant treatment in that population (diuretics, bronchodilators, corticosteroids)

The five levels will then be reduced to three (1 and 2: high probability; 3: intermediate probability; 4-5: low probability), to concord with the protocol. The diagnostic threshold will separate 1-3 from 4-5.

If pneumonia is rated as excluded or unlikely, the experts will be asked to propose an alternative diagnosis for the symptoms of the patient: congestive heart failure, exacerbation of COPD, other

non-pneumonic respiratory infection (acute bronchitis), pulmonary malignancy, interstitial lung disease, pneumothorax, other

If pneumonia is rated as possible, probable or very likely, the experts will be asked two further questions:

- 'Do you think it is aspiration pneumonia (Y/N)
- "Do you think it is a viral pneumonia (i.e. without bacterial superinfection Y/N) if pneumonia is possible, probable or certain?

**5/ Validity and reproducibility** of the diagnosis: agreement between groups of experts will be assessed in a random sample of patients

